6.2 Nonserious Adverse Events

A *nonserious adverse event* is an AE not classified as serious.

6.2.1 Nonserious Adverse Event Collection and Reporting

The collection of nonserious AE information should begin at initiation of study drug until 100 days from the last dose of study drug. Nonserious AE information should also be collected from the start of a placebo lead-in period or other observational period intended to establish a baseline status for the subjects.

Nonserious AEs should be followed to resolution or stabilization, or reported as SAEs if they become serious (see [Section 6.1.1](#)). Follow-up is also required for nonserious AEs that cause interruption or discontinuation of study drug and for those present at the end of study treatment as appropriate. All identified nonserious AEs must be recorded and described on the nonserious AE page of the CRF (paper or electronic).

Completion of supplemental CRFs may be requested for AEs and/or laboratory abnormalities that are reported/identified during the course of the study.

6.3 Laboratory Test Result Abnormalities

The following laboratory test result abnormalities should be captured on the nonserious AE CRF page or SAE Report Form (paper or electronic) as appropriate:

- Any laboratory test result that is clinically significant or meets the definition of an SAE
- Any laboratory test result abnormality that required the subject to have study drug discontinued or interrupted
- Any laboratory test result abnormality that required the subject to receive specific corrective therapy.

It is expected that wherever possible, the clinical rather than laboratory term would be used by the reporting investigator (eg, anemia versus low hemoglobin value).

6.4 Pregnancy

If, following initiation of the study drug, it is subsequently discovered that a study subject is pregnant or may have been pregnant at the time of study exposure, including during at least 5 half lives after product administration, the investigator must immediately notify the BMS Medical Monitor/designee of this event and complete and forward a Pregnancy Surveillance Form to BMS Designee within 24 hours of awareness of the event and in accordance with SAE reporting procedures described in Section 6.1.1.

In most cases, the study drug will be permanently discontinued in an appropriate manner (eg, dose tapering if necessary for subject safety).

In the rare event that the benefit of continuing study drug is thought to outweigh the risk, after consultation with BMS, the pregnant subject may continue study drug after a thorough discussion of benefits and risk with the subject

The investigator must immediately notify the BMS (or designee) Medical Monitor of this event and complete and forward a Pregnancy Surveillance Form to BMS (or designee) within 24 hours of awareness of the event and in accordance with SAE reporting procedures described in [Section 6.1.1](#).

Follow-up information regarding the course of the pregnancy, including perinatal and neonatal outcome and, where applicable, offspring information must be reported on the Pregnancy Surveillance Form.

Any pregnancy that occurs in a female partner of a male study participant should be reported to BMS. Information on this pregnancy will be collected on the Pregnancy Surveillance Form.

6.5 Overdose

An overdose is defined as the accidental or intentional administration of any dose of a product that is considered both excessive and medically important. All occurrences of overdose must be reported as an SAE (see Section 6.1.1 for reporting details.).

6.6 Potential Drug Induced Liver Injury (DILI)

Wherever possible, timely confirmation of initial liver-related laboratory abnormalities should occur prior to the reporting of a potential DILI event. All occurrences of potential DILIs, meeting the defined criteria, must be reported as SAEs (see Section 6.1.1 for reporting details).

Potential drug induced liver injury is defined as:

1. AT (ALT or AST) elevation > 3 times upper limit of normal (ULN)
AND
2. Total bilirubin > 2 times ULN, without initial findings of cholestasis (elevated serum alkaline phosphatase),
AND
3. No other immediately apparent possible causes of AT elevation and hyperbilirubinemia, including, but not limited to, viral hepatitis, pre-existing chronic or acute liver disease, or the administration of other drug(s) known to be hepatotoxic.

6.7 Other Safety Considerations

Any significant worsening noted during interim or final physical examinations, electrocardiogram, x-ray filming, any other potential safety assessment required or not required by protocol should also be recorded as a nonserious or serious AE, as appropriate, and reported accordingly.

7 DATA MONITORING COMMITTEE AND OTHER EXTERNAL COMMITTEES

Not Applicable.

8 STATISTICAL CONSIDERATIONS

8.1 Sample Size Determination

- In the Dose Evaluation Phase (Cohort A), 6 -12 subjects will be treated (Section 4.5.1). The number of subjects is not based on statistical power considerations. If less than 1/3 of 6 subjects experience a DLT, the upper limit of the 80% 1-sided exact confidence interval for the true DLT rate will not be greater than 42%. If less than 1/3 of 12 subjects experience a DLT, the upper limit of the 1-sided 80% exact confidence interval (CI) for the true DLT rate will not be greater than 41.2%.
- In the Expansion Phase (Cohort B), a total of 130 subjects will be treated, with 40 subjects in cohort B1 (DLBCL), 30 subjects in cohort B2 (PTCL), 20 subjects in B3 (CTCL), 30 subjects in cohort B4 (PMBL) and 10 subjects in cohort B5 (MGZL).
 - Given 40 subjects in DLBCL, the one-sided 90% confidence interval (ie, two-sided 80% confidence interval) for the ORR is 48.6% - 70.6% if we assume an observed ORR rate of 60%. The lower bound of the 90% CI excludes 40%, which is the null hypothesis ORR rate for PTCL.
 - Given 30 subjects in PTCL, the one-sided 90% confidence interval (ie, two-sided 80% confidence interval) for the ORR is 46.7% - 72.3% if we assume an observed ORR rate of 60%. The lower bound of the 90% CI excludes 40%, which is the null hypothesis ORR rate for PTCL.
 - Given 20 subjects in CTCL, the one-sided 90% confidence interval (ie, two-sided 80% confidence interval) for ORR is 63.9% - 91.0% if we assume an observed ORR rate of 80%. The lower bound of the 90% CI excludes 60%, which is the null hypothesis ORR rate for CTCL.
 - Given 30 subjects in PMBL, the one-sided 90 % confidence interval (ie, two-sided 80% confidence interval) for the ORR is 37.0% - 63.0% if we assume an observed ORR rate of 50%. The lower bound of the 90% CI excludes 30%, which is the null hypothesis ORR rate for PMBL.
 - Given 10 subjects in MGZL, the one-sided 90 % confidence interval (ie, two-sided 80% confidence interval) for the ORR is 11.6% - 55.2% if we assume an observed ORR rate of 50%. The lower bound of the 90% CI excludes 10%, which is the null hypothesis ORR rate for MGZL.

Table 8.1-1 summarizes the 90% exact CI for different targeted ORRs and sample sizes. The targeted ORR of 60% in DLBCL and PTCL and 80% in CTCL, and null hypothesis ORR rate of 40% in DLBCL and PTCL and 60% in CTCL are based on the historical data and the activity of brentuximab vedotin and nivolumab as single agents from phase I and phase II studies.
[19,39,86,87](#)

Table 8.1-1: One-sided 90% Exact CI for different number of subjects in each cohort		
	If the observed ORR rate is 60% in Cohort B1 and B2	Power
N=30	[46.7% - 72.3%]	82%
N=40	[48.6% - 70.6%]	87%
If the observed ORR rate is 80% in Cohort B3		
N=20	[63.9% - 91.0%]	62 %
If the observed ORR rate is 50% in Cohort B4		
N=30	[37.0% - 63.0%]	81 %
If the observed ORR rate is 30% in Cohort B5		
N=10	[11.6% - 55.2%]	61%

Also, If we have 20 subjects in Cohort B3, assuming true ORR is 80%, there will be approximately 62% power to reject null hypothesis that the true ORR is $\leq 60\%$, considering a one-sided alpha of 10%. Given a very low prevalence of CTCL, 20 subjects in cohort III is considered as feasible and adequate for a phase II signal detecting trial. Sample size of 30 subjects in Cohort B2 and 40 subjects in Cohort B1 are corresponding to power of 82% and 87% respectively to reject null hypothesis that the true ORR is $\leq 40\%$ assuming true ORR is 60% and considering a one-sided alpha of 10%. If we have 30 subjects in Cohort B4, assuming true ORR is 50%, there will be approximately 81% power to reject null hypothesis that the true ORR is $\leq 30\%$, considering a one-sided alpha of 10%. Finally if we have 10 subjects in Cohort B5, assuming true ORR is 30%, there will be approximately 61% power to reject null hypothesis that the true ORR is $\leq 10\%$, considering a one-sided alpha of 10%.

If the screening failure rate is 20%, we would need to enroll 170 subjects to have 136 patients treated (130 in Cohort B, 6 in Cohort A). If Cohort A needs 6-12 more treated subjects, we would need to enroll 8-15 more subjects accordingly.

8.2 Populations for Analyses

In each cohort the following populations will be defined:

- All Enrolled Subjects: All subjects who signed an informed consent form and were registered into the IVRS.
- All Treated Subjects: All subjects who received at least one dose of any of the study drugs. This is the primary population for safety and efficacy analyses. This dataset will be used for baseline demographics and efficacy and safety analyses.
- PK Subjects: Subjects with available serum time-concentration data from treated subjects dosed with nivolumab and/or brentuximab vedotin.
- HEOR subjects: treated subjects who have an assessment at screening/baseline and at least 1 follow-up assessment

- Immunogenicity subjects: treated subjects who have an assessment at screening/baseline and at least 1 follow-up assessment

8.3 Endpoints

8.3.1 Primary Endpoint(s)

The primary safety endpoints include incidence of deaths, adverse events, serious adverse events, adverse events leading to discontinuation, adverse events leading to dose delay, drug-related adverse events and specific laboratory abnormalities (worst grade). Toxicities will be graded using the National Cancer Institute (NCI) Common Terminology Criteria for Adverse Events (CTCAE) version 4.03.

The primary efficacy endpoint is ORR. It is defined as the number of subjects with a best overall response (BOR) of confirmed CR or PR divided by the number of treated subjects. The BOR is defined as the best response designation recorded between the date of first dose and the date of initial objectively documented progression or the date of subsequent therapy, whichever occurs first. Allogeneic SCT and ASCT will be considered as subsequent therapy. In subjects with relapsed refractory DLBCL, relapsed refractory PTCL, relapsed refractory PMBL and relapsed refractory MGZL the response (CR, PR, PD, and progression) will be assessed according to Lugano Classification 2014. For subjects with relapsed refractory CTCL, response will be assessed according to consensus Global Response Score as per the consensus statement of the International Society for Cutaneous Lymphoma. A CR must have been confirmed by scans, including a negative Positron Emission Tomography (PET) to be considered for CR in subjects with PTCL, DLBCL, PMBL and MZGL. In subjects with PTCL, if the bone marrow was compromised at baseline, a bone marrow must also be negative at the time of CR. In CTCL CT scans (chest, neck, abdomen and pelvis), blood flow for SS cells and m SWAT skin scoring along with medical photography will be performed at baseline and at the end of the treatment for response evaluation. The investigator will perform tests that will allow evaluation of response to therapy according to corresponding disease criteria in [Appendix 2](#) and [Appendix 4](#). The analysis of the primary endpoint will occur approximately 8 months after the last enrolled subject's first dose of study therapy. Depending on the enrollment for each disease cohort, the analysis may be done at different times for each cohort, or at the same time for the three cohorts.

8.3.2 Secondary Endpoint(s)

The secondary endpoints are DOR, CR rate, duration of CR, PFS and OS.

DOR will be calculated from the date of initial documentation of a response (CR, or PR) to the date of first documented evidence of progressive disease (or relapse for subjects who experience CR during the study) or death. Subjects who are progression-free and alive or have unknown status will be censored at the last tumor assessment. For subjects who received subsequent therapy prior to documented progression, duration of response will be censored on the last tumor assessment date prior to subsequent therapy. Allogeneic SCT and ASCT will be considered as subsequent therapy.

The CR rate is defined as the number of subjects with a BOR of CR divided by the number of treated subjects. The duration of CR will only be evaluated in subjects with BOR of CR and is defined as the time from first documentation of CR to the date of initial documented progression or death due to any cause, whichever occurs first. Censoring will be applied as per DOR definition.

PFS is defined as the time from the date of first dose of study drug until the date of first documented evidence of progressive disease (or relapse for subjects who experience CR during the study) or death, whichever comes first. Subjects who are progression-free and alive or have unknown status will be censored at the last tumor assessment. For subjects who received subsequent therapy prior to documented progression, it will be censored on the last tumor assessment date prior to subsequent therapy.

OS is defined as the time from the date of first dose of study drug until the date of death (any reason). If the subject is alive or the vital status is unknown, the subject will be censored at the date the subject was last known to be alive.

8.3.3 Exploratory Endpoint(s)

The Indeterminate response will be assessed per the Lymphoma Response to Immunomodulatory therapy Criteria (LYRIC). The exploratory biomarker objectives are to assess CD30 expression and correlate with response, and to assess PD-L1/L2 status and correlate it with response etc. These biomarker endpoints are discussed in detail in [Section 5.6](#). The exploratory objectives also include characterizing pharmacokinetics (PK) and the immunogenicity of nivolumab and brentuximab vedotin following combination therapy. The nivolumab and brentuximab vedotin concentration, PK parameter and immunogenicity endpoints are discussed in details in [Section 5.5](#).

8.4 Analyses

8.4.1 Demographics and Baseline Characteristics

Demographic and baseline characteristics of patient will be summarized for each cohort and also for all treated subjects.

8.4.2 Efficacy Analyses

All analyses will be performed separately for each cohort and also for all treated subjects combined with same treatment dosage (ie, safety cohort subjects with different dose from the expansion cohort will not be combined).

The ORR will be summarized by binomial response rates and their corresponding two-sided 80% exact CIs using the Clopper-Pearson method. The same analysis will be performed for CR rate.

The DOR will be summarized by cohort for subjects who achieve confirmed PR or CR using the Kaplan-Meier (KM) product-limit method. Median values of DOR, along with two-sided 95% CI using log-log transformation method and range, will also be calculated. The same analysis will be performed for duration of CR, PFS and OS at 1 year. Detailed analyses on efficacy endpoints will be presented in the statistical analyses plan.

8.4.3 Safety Analyses

Safety analyses will be performed in all treated subjects. Descriptive statistics of safety will be presented using National Cancer Institute (NCI) Common Terminology Criteria for Adverse Events (CTCAE) version 4.03. All on-study AEs, drug-related, AEs, SAEs and drug-related SAEs will be tabulated using worst grade per NCI CTCAE v4.03 criteria by system organ class and MedDRA preferred term. On-study lab parameters including hematology, chemistry, liver function, thyroid function, and renal function will be summarized using worst grade per NCI CTCAE v4.03 criteria.

In addition to separate analyses per cohort, safety analyses will be performed all treated subjects combined. If safety cohorts subject have different doses, the safety results will be presented by cohorts and by dose.

8.4.4 Pharmacokinetic Analyses

The nivolumab and brentuximab vedotin concentration data obtained in this study may be combined with data from other studies in the clinical development programs to develop or refine existing population PK models. These models may be used to evaluate the effects of intrinsic and extrinsic covariates on the PK of nivolumab or brentuximab vedotin and to determine measures of individual exposure (such as steady-state peak, trough, and time-averaged concentration). In addition, model determined exposures may be used for exposure-response analyses. Results of population PK and exposure response-analyses will be reported separately.

8.4.5 Biomarker Analyses

Summary statistics for peripheral blood and tumor biomarker activity such as, but not limited to CD30, PD-L1/L2 expression levels and their corresponding changes (or percent changes) from baseline will be tabulated by planned study visit to assess pharmacodynamic effects. In addition, the time course of biomarker outcomes will be investigated graphically; if there is indication of meaningful pattern across time, further analysis may be performed to characterize the relationship. Results from peripheral blood and tumor biomarkers will be tabulated and associations between biomarkers and efficacy or safety measures will be assessed. Methods such as, but not limited to, logistic regression will be used to explore possible associations between measures of peripheral blood, tumor biopsies and clinical outcome. More details of biomarker analyses will be described in the statistical analysis plan.

8.4.6 Outcomes Research Analyses

Subject's overall health state on a visual analog scale (EQ-VAS) at each assessment time point will be summarized using descriptive statistics (N, mean, standard deviation, median, first and third quartiles, minimum, maximum). Proportion of subjects reporting problems for the 5 EQ-5D 3L dimensions at each assessment time point will be summarized by level of problem. Percentages will be based on number subjects assessed at assessment time point.

A by-subject listing of EQ-5D 3L with the problem levels for each of the 5 dimensions (mobility, self-care, usual activities, pain/discomfort and anxiety/depression), health state (5 dimensions digits combined in a 5-digit number) and EQ-VAS will be provided.

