1.3.3 Exploratory Objectives

- To assess the Indeterminate response (IR) per Lymphoma Response to Immunomodulatory therapy Criteria (LYRIC)⁸⁵ in subjects with DLBCL, PTCL, PMBL, MGZL and CTCL (if applicable).
- To assess CD30 expression and correlate with response, and to assess PD-L1/L2 status and correlate it with response.
- To characterize the molecular effects of the brentuximab vedotin and nivolumab combination regimen on tumor cells and the immune response; and identify biomarkers of response or resistance to the combination.
- To assess tumor microenvironment and peripheral immune status
- To characterize pharmacokinetics of nivolumab and brentuximab vedotin and explore exposure-response relationships.
- To characterize the immunogenicity of nivolumab and brentuximab vedotin following combination therapy.
- To evaluate changes in general health status assessed by the EQ-5D 3L (Cohort B only).

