The Expansion Phase will consist of a single-arm phase II study which will expand enrollment at the recommended dose level and treatment schedule as deemed safe by the study team in Cohort A. An additional 40 subjects in DLBCL (cohort B1), 30 subjects in PTCL (cohort B2) 20 subjects in CTCL (cohort B3), 30 subjects in PMBL (cohort B4) and 10 subjects in MGZL (cohort B5) will be enrolled to complete this evaluation.

If one or none (≤ 1) of the 6 subjects in cohort A experience a DLT, the expansion cohort will begin with brentuximab vedotin 1.8 mg/kg Cycle 1 Day 1 and nivolumab 240 mg flat dose on Cycle 1 Day 8. Subsequent to cycle 1, both drugs will be administered on the first day of the new cycle. Brentuximab vedotin will be administered first as a 30-minute infusion followed by a minimum 30-minute rest. Nivolumab will be then be administered as a 30-minute infusion. If two or more (≥ 2) of the 6 subjects are determined to have had a DLT based on the protocol definition (refer to [section 4.5.1](#)) treatment modification or enrollment closure will be considered, as described above.

All subjects in the study (Cohort A and Cohort B) will be allowed to be treated until disease progression or unacceptable toxicity as described in [Section 4.5.3](#) and [Section 4.5.5](#). If during therapy it appears that a subject is benefiting from the combination but experiencing toxicities related to one agent that would require permanent treatment discontinuation, then they have the option to continue therapy with the single agent not attributing to toxicities.

[figure not shown]
Subjects that present progressive disease during treatment may be allowed to be treated beyond progression until further progression is observed. Refer to [Section 4.5.9](#) for further details.

Once subjects discontinue from study treatment for any reason, subjects will enter the follow-up phase of the study. During follow-up long-term safety, survival status, disease progression, subsequent anticancer therapy and occurrence of other primary malignancy data will be collected. Follow-up visit 1 (X01) and follow-up visit 2 (X02) will be in person visits and all subsequent

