				All windows proposed are calendar days. Procedures must be done within 72h prior to dosing unless otherwise specified.
Bone Marrow Aspirate and Biopsy			See Note	Bone Marrow assessment is not required for DLBCL/CTCL/PMBL/MGZL subjects unless clinically indicated. It is recommended for PTCL subjects if there is clinical suspicion for disease involvement in the bone marrow. If a biopsy and/or aspirate is performed during treatment, submission for biomarker analyses is optional. Refer to Table 5.6-1 for further details. Required to confirm complete response (CR) in subjects with bone marrow disease at screening.
Additional Biomarker Samples • Tumor biopsy • Blood	See Note	See Note	See Note	See Table 5.6-1 for collection of samples for biomarker studies
Outcomes Research Questionnaire				
EQ-5D 3L Questionnaire	X		X	Subjects will be asked to complete the EQ-5D 3L prior to study drug administration and before any clinical activities. Refer to section 5.7 for more information. To be completed only for subjects enrolled in the Expansion Phase (Cohort B).
PK and Immunogenicity Assessments				
PK and Immunogenicity Samples				See Table 5.6-1 for sampling details.

Table 5.1-2: On Treatment Procedures (CA209436)				
	On treatment procedures			
Procedure	Cycle 1 Day 1	Cycle 1 Day 8	Cycle 2 & Beyond, Day 1	Notes
All windows proposed are calendar days. Procedures must be done within 72h prior to dosing unless otherwise specified.				
Clinical Drug Supplies				
Administer Study Drug	Brentuximab vedotin	Nivolumab	X	
Brentuximab vedotin will be administered at C1D1 and Nivolumab will be administered on C1D8. At all subsequent cycles, both study drugs will be administered on the same day. Brentuximab vedotin will be administered first followed by a minimum 30 minute rest. Nivolumab will be administered second. Refer to Section 4.5 for further details.
 
IVRS should be called within 3 days prior to study drug administration to receive vial assignment.

Table 5.1-3: Follow-up Assessments (CA209436)			
Follow-up Assessments (CA209436)			
Procedure	Follow Up, Visits 1 and 2^a (X01 & X02)	Survival Follow-Up Visits^b	Notes
Safety Assessments			
Targeted Physical Examination	X		Lymph node areas (eg, submandibular, cervical, supraclavicular, axillary, or inguinal lymph node), abdominal organs (eg, spleen) and neurological examination Skin evaluation with mSWAT scoring in CTCL
Adverse Events Assessment	X		

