GVHD Assessments			Only for subjects who proceed to allogeneic SCT. To be assessed on Day 100, at 6 months, at 1 year and every 1 year thereafter from the date of stem cell infusion until the first non-CR after SCT is documented. Refer to Appendix 5 for further details.
Subsequent Anticancer Therapy	X	X	
Other Primary Malignancies	X	X	
Biomarker Assessments			
Serum, Tumor Biopsy, Bone Marrow Aspirate/biopsy	See Note		Optional biomarker samples collected at time of progression. See Table 5.6-1 for biomarker sampling details
Pharmacokinetic/Immunogenicity Assessments			
PK and Immunogenicity samples	X		See Table 5.5.1-1 for PK and immunogenicity sampling details
Outcomes Research Assessments			
EQ-5D 3L Questionnaire	X	X	EQ-5D-3L questionnaires administered during survival follow-up will be completed in clinic or via phone contact. Refer to section 5.7 for more information. To be completed only for subjects enrolled in the Expansion Phase (Cohort B).

Table 5.1-3: Follow-up Assessments (CA209436)			
Follow-up Assessments (CA209436)			
Procedure	Follow Up, Visits 1 and 2^a (X01 & X02)	Survival Follow-Up Visits^b	Notes
Subject Status			
Survival Status	X	X	Survival follow-up visits are expected to occur every 3 months after X02; may be accomplished by visit, phone contact or email, to update survival information and assess subsequent anti-cancer therapy. BMS may request that survival data be collected on all treated subjects outside of the 3 month specified window. At the time of this request, each subject will be contacted to determine their survival status unless the subject has withdrawn consent for all contact.

^a Follow-up visit 1 (X01) = 35 days from the last dose +/- 7 days. Follow-up visit 2 (X02) = 80 days (+/- 7 days) from follow-up visit X01.

^b Survival Follow-up visits to occur every 3 months from X02. BMS may request that survival data be collected on all treated subjects outside of the 3 month specified window. At the time of this request, each subject will be contacted to determine their survival status unless the subject has withdrawn consent for all contact.

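### The exploratory EQ-5D objective is change in health status, but protocol 8.4.6 plans only levels among those assessed at each visit, which mix change with a changing set of subjects

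*Protocol*

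**What the plan says.** **Objective.** Protocol 1.3.3 lists, as an exploratory objective, "To evaluate changes in general health status assessed by the EQ-5D 3L (Cohort B only").

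**Analysis.** Under protocol 8.4.6 the EQ-VAS "at each assessment time point will be summarized using descriptive statistics" (N, mean, SD, median, quartiles, range). Each of the five dimensions is summarised by level of problem, and "Percentages will be based on number subjects assessed at assessment time point". The section adds "A by-subject listing of EQ-5D 3L with the problem levels for each of the 5 dimensions", together with the combined health state and the EQ-VAS. It states no change or shift from baseline, no completion rate and no handling of missing assessments.

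**Population.** Protocol 8.2 defines "HEOR subjects: treated subjects who have an assessment at screening/baseline and at least 1 follow-up assessment". Section 8.4.6 does not name this set.

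**Collection.** EQ-5D is due on Cycle 1 Day 1 and on Day 1 of every later cycle (Table 5.1-2): "Subjects will be asked to complete the EQ-5D 3L prior to study drug administration and before any clinical activities". After treatment it is due at X01, X02 and the survival visits (Table 5.1-3): "EQ-5D-3L questionnaires administered during survival follow-up will be completed in clinic or via phone contact".

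**Leaving the cycle visits.** Under protocol 3.1, subjects in both cohorts "will be allowed to be treated until disease progression or unacceptable toxicity as described in" Sections 4.5.3 and 4.5.5.

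**The concern.** The objective asks how health status changes, and none of the statistics in 8.4.6 is a change. A reader would have to infer change by comparing one visit's mean or percentage with the next, and those come from different sets of people. The main reasons for stopping treatment, progression and toxicity, are plausibly related to health. If subjects in poorer health leave the cycle visits first, the mean EQ-VAS of those remaining drifts up and the percentage with problems drifts down, even if no individual changes.

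X01 and X02 are timed from the last dose. An X01 summary therefore pools subjects who stopped early with subjects who stopped late, and it cannot be joined to the cycle series on a common time axis. With no control arm, there is also no comparator with similar attrition against which to judge a trend. What is at stake is the interpretation of one exploratory endpoint: a flat or rising on-treatment series could be taken as maintained or improved health status.

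**Working it through.** **1. Objective against analysis.** The protocol gives no EQ-5D sample size, SD, expected dropout or effect, so there is no planned figure to reproduce. Setting the sections side by side:

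- 1.3.3 asks for change; 8.4.6 gives levels per time point and a listing.
- 8.4.5, the section before, does plan changes or percent changes from baseline for biomarkers.
- 8.2 defines a set that requires a baseline and a later value, which suits a change analysis; 8.4.6 does not use it.
- 8.4.2, 8.4.5 and 8.4.7.1 each refer to the SAP for detail; 8.4.6 does not.

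Followed as written, the protocol text yields no summary of the stated objective.

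**2. How far selection alone could move an EQ-VAS mean (illustration; every input is assumed).** Let SD be the baseline EQ-VAS SD (20), d the share off treatment, and r the correlation between EQ-VAS and an underlying tendency to stay on treatment. Both are taken as normal, ignoring the 0-100 limits. With no within-subject change,

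shift in the per-visit mean = r × SD × φ(z_d) / (1 − d),

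where z_d is the standard normal d-quantile. For d = 50% and r = 0.3: 0.3 × 20 × 0.3989 / 0.5 = 4.79.

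| r | d = 25% | d = 50% | d = 75% |
|---|---|---|---|
| −0.3 | −2.5 | −4.8 | −7.6 |
| 0 | 0 | 0 | 0 |
| 0.1 | +0.9 | +1.6 | +2.5 |
| 0.3 | +2.5 | +4.8 | +7.6 |
| 0.5 | +4.2 | +8.0 | +12.7 |

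A simulation of 400,000 subjects agrees (for example +4.74 at d = 50%, r = 0.3). The paired change is 0 in every case, but only because no change was put in.

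**3. With a true decline.** If everyone falls by 5 points, subtract 5 from the table. At r = 0.3 the per-visit shift is −2.5, −0.2 and +2.6 at d = 25%, 50% and 75%. With a 10-point fall it is −7.5, −5.2 and −2.4. The displayed mean may therefore rise, stay flat or fall; in these cases it understates the decline.

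**4. The dimension percentages.** Assume that half of subjects report a problem at baseline, that no one changes, and that those with a problem are RR times as likely to have left. The percentage with a problem among those remaining is p(1 − RR·q0)/(1 − d), with q0 = d/(p·RR + 1 − p). For d = 50% and RR = 1.5: q0 = 0.5/1.25 = 0.4, giving 0.5 × (1 − 0.6)/0.5 = 40% instead of 50%. At d = 25% and RR = 1.5 it is 46.7%; at d = 50% and RR = 2 it is 33.3%.

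**5. Does pairing cure it?** Not fully. Suppose leaving depends on the change itself (assumed change SD 15, true mean change −5, d = 50%). The paired change in those remaining is about −5 + r × 15 × 0.798, which is −1.4 at r = 0.3 and +1.0 at r = 0.5. Pairing removes the part of the bias due to differing baseline levels, but not the part due to leaving because of deterioration.

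**The case against.** Several counter-arguments have force.

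- **Direction is not settled.** A reader might infer that on-treatment scores must improve by construction. The documents do not support that. A rise needs leaving to be related to health status and the selection effect to exceed any true decline; at r = 0 there is no shift. Some exits may select the other way: subjects can leave for allogeneic or autologous transplant (3.6, 4.5.5), and these may be responders in better health. Some progressors stay on cycle visits under 4.5.9, and toxicity from one drug may lead to continuing the other alone. This objection stands.
- **The SAP may cover it.** The public copy passes from 7.8.2.2 to 7.10 and shows no exploratory objectives or HEOR population. A reader might infer that no change analysis exists anywhere; that cannot be concluded. The point is limited to the protocol text.
- **The plan already mitigates.** N is reported for the EQ-VAS, so a shrinking group is visible. Collection continues after discontinuation, and a listing is planned. All this is true, and it means the data would support a change analysis. But a listing derives nothing, and N shows how many remain, not how they differ from those who left.
- **Proportionality.** The endpoint is exploratory and descriptive, with no test or decision attached. In cohorts of 40, 30, 20, 30 and 10, a mixed model is a debatable extra. This stands, and it limits both the severity and the remedy.

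**Conclusion.** The mismatch holds for the protocol: the objective is change, and 8.4.6 states no summary of change although the data and a suitable population are already specified. The on-treatment summaries combine within-subject change with a changing set of subjects, and they may be biased upward or mask a decline.

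Size and direction cannot be determined from the documents. The figures above (for example +4.8 EQ-VAS points at SD 20, half off treatment, r = 0.3) rest wholly on assumed inputs and only show that a shift of several points is possible. They do not predict this trial's result. Severity is minor, since ORR and the safety analyses are unaffected.

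**What to change.** In 8.4.6, and in the SAP if it is not already there:

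1. Add mean EQ-VAS change from baseline, and a shift table from baseline for each of the five dimensions, in the HEOR subjects defined in 8.2.
2. Give N and completion (assessed/expected) at each time point, and define who counts as expected on treatment and in follow-up.
3. Show the X01, X02 and survival assessments alongside the on-treatment ones, for example by time since first dose. This needs stated visit windows, because X01 and X02 are timed from the last dose.
4. Keep the per-visit tables as descriptive.
5. State that paired change among those remaining is still open to bias from informative dropout. A mixed model for EQ-VAS could be an optional sensitivity analysis, no more.

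The cost is modest programming, with no new data collection. The reported trend may turn out less favourable than the per-visit means.
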